5.0 Study Procedures

5.1 Study Design

Research Design: A multi-center, repeat-measures randomized controlled mixed-methods trial.

Study Population: The proposed study will focus on Internal Medicine physicians who are part of inpatient care teams and nurses providing care on medical and medical/surgical units at LTC Charles S. Kettles VAMC in Ann Arbor, MI and MEDVAMC in Houston, TX. Medical students, surgical physicians, and physicians on sub-specialty teams will not be included. At both participating facilities the inpatient care teams are predominately composed of 1 attending, 1 senior resident, 2 interns, and up to 3 medical or physician assistant students. Interns and senior residents are usually assigned to a team for 4-week blocks (occasionally 2 weeks), while attendings rotate approximately every 2 weeks. The Ann Arbor VAMC has 3 medical or medical/surgical inpatient units, while MEDVAMC has 5 units. At both facilities each nursing unit employs between 20-30 nurses. We will aim to recruit approximately 30 attendings, 72 residents and 40 nurses at Ann Arbor VAMC. As MEDVAMC is larger, with a greater number of inpatient care teams and nursing units than the Ann Arbor VAMC, we will aim to recruit approximately 40 attendings, 72 residents and 90 nurses. Our target study sample size is a total of 344 physicians and nurses (167 intervention/177 control). For Aim 3, we plan to interview approximately 8 physician team members and 4-6 nurses from the intervention arm at each site.

General Study Overview and Outcome Measures:

A summary of the proposed study activities at each participating site is presented in **Table 2** below.

Table 2: Overview of Study Activities at Each Study Site

| Study Detail | Physicians | Nurses |
|----------------------------------|--|--|
| Target | Attendings, senior residents and interns on inpatient medicine teams | Nurses on medical or medical/surgical units |
| Teams/Units Participating | 2 teams each month for 12 months randomized to intervention or control arm at each site | 2 units (1 intervention; 1 control) at Ann Arbor VAMC & 4 units (2 intervention; 2 control) at MEDVAMC randomized once & followed for 12-months |
| Estimated number of participants | 107 intervention and 107 control | 20 intervention and 20 control at Ann Arbor VAMC; 40 intervention and 50 control at MEDVAMC |
| Habituation Period | 1 month | 1 month |

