| Habituation assessment | 
 Unit-based hand hygiene observations | 
 Unit-based hand hygiene observations |
| Pre-Intervention Assessment | 
 Survey (FFMQ, WBI, select PSHW) | 
 Survey (FFMQ, WBI, select PSHW) |
| Intervention Period | 2-4 weeks | 1 month |
| Intervention Assessment | 
 Hand hygiene observations Survey given at end of intervention (FFMQ, WBI, select PSHW) Mobile app data and usage Completion of STREAM mindfulness modules Transcripts from intervention guided discussions Qualitative interviews with ~8 physicians per site | 
 Hand hygiene observations Survey given at end of intervention (FFMQ, WBI, select PSHW) Mobile app data and usage Completion of STREAM mindfulness modules Transcripts from intervention guided discussions Qualitative interviews with ~4-6 nurses per site |
| 6-month Follow-up | 
 Emailed survey (FFMQ, WBI, select PSHW) | 
 Survey emailed or given in person (FFMQ, WBI, select PSHW) |
| Sustainability follow-up | 
 Select hand hygiene observations for ~10 weekdays at 3-12 months follow-up | 
 Hand hygiene observations for 1 month at 12 months follow-up |

Habituation Period - To collect baseline data on hand hygiene adherence and duration and to habituate providers to the presence of observers, 1 month of covert, unit-based hand hygiene observations will be conducted. At the end of year 1, we will report out on observed hand hygiene rates. Observation of hand hygiene adherence will include hand hygiene prior to patient room entry and after exiting the patient room (**Appendix A**). In US hospitals, the entry/exit method has been demonstrated to be feasible for observed hand hygiene adherence monitoring by overcoming line-of-sight issues and other barriers.⁷⁴ Hand hygiene observers will not enter patient rooms or interfere in patient care. Observation of hand hygiene duration will be done when providers exit patient rooms, as observing hand hygiene duration upon room entry will not be feasible

since observers will not enter patient rooms.

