Covert observations within randomly selected areas within units will also be conducted for observing hand hygiene among nurse participants. Observations will be conducted for 1 month before the intervention and 1-month after the intervention. On all participating units, observations of nurse hand hygiene while entering and exiting patient rooms will be conducted. Hand hygiene duration among all nurses will also be captured upon room exit. Nurses will be observed for approximately 4 hours per day during the first part of their shift, as all nurses typically check in with each patient at the start of their shift. From covert locations within the unit, the observers will only be able to observe approximately 10 rooms at a time. They will move their location in the unit each day to ensure representation from different nurses. The number of times a nurse enters each patient room will vary, but we estimate at minimum each nurse will enter each room once per hour. Therefore, observing 10 patient rooms for 4 hours per day, with 2 observation points per entry would lead to approximately 80 hand hygiene moments observed per day per unit. Observing 3 units per arm for approximately 44 days total would lead to an estimated 7,040 nurse hand hygiene observations per study arm in total. As hand hygiene duration will also be recorded upon room exit, and estimated total of 3520 hand hygiene duration observations per study arm will be observed. In addition to the 1-month post-intervention observation period, we will also observe and collect 1 month of data on hand hygiene moments at 1-year post-intervention in the intervention and control units at both sites.

Collected data will be transferred from the paper observation data tool into a study database. The data analyst and project manager will be able to link these covert observations accordingly to intervention or control groups based on team and unit name.

Study surveys will be distributed in person using a paper survey and a postage-paid business reply envelope where feasible. Electronic surveys containing questions from FFMQ, WBI, and PSHW surveys will be generated. Study participants will be directed to a link to the survey tool (for the pre- and post-intervention, as well as 6-month post-intervention follow-up periods) and responses will be saved to a database managed by the study team.

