5.6 Data Analysis

Quantitative Statistical Analysis (Aims 1 and 2): Differences in hand hygiene adherence and duration between intervention and control groups will be assessed using Fisher's exact test and t-test, as appropriate. Risk differences in adherence to duration of hand hygiene will be calculated for both intervention and control groups. Because the primary outcomes for Aim 1 (i.e., hand hygiene adherence and duration) are expected to occur frequently, we will use generalized linear models to evaluate differences in hand hygiene adherence and duration for the intervention versus control group, with the Poisson distribution (log link) and robust error variance. Models will account for provider type and level, and will incorporate clustering by physician team (and separately for nursing unit). Statistical significance will be calculated for the intervention (intervention vs. control) coefficient.

As a secondary outcome for Aim 1, we will assess changes and differences in hand hygiene perception based on response to select questions from PSHW. For Aim 2, mindfulness will be based on responses to FFMQ and well-being will be based on responses to WBI. FFMQ and WBI scales will be scored according to the published algorithms. Descriptive statistics will be used to summarize participant scores from pre- and post-intervention, as well as 6-month post-intervention follow-up assessments. Within-group paired-samples t-tests will be used to test for improvement in participant scores across the baseline, post-intervention (~14 days for physicians and 1-month for nurses), and 6-month post-intervention follow-up periods, for the intervention and control groups separately. Analyses will use list-wise deletion for missing data. Participants not completing all surveys will still be included in any analysis for which they provide data. For all analyses, p values less than 0.05 will be considered significant and all tests will be two-tailed. Analysis of covariance (ANCOVA) models will then be used to assess relative changes in mindfulness, well-being, and hand hygiene perceptions across groups, the most direct test of discriminant validity. In these models, post-test scores will be predicted by group status controlling for pre-test scores.

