Mindful Hand Hygiene to
Reduce Infections Among
Veterans While Enhancing
Provider Well-Being

NCT05261282

December 5, 2025

Data Analysis Plan

Differences in hand hygiene adherence and duration between intervention and control groups will be assessed using Fisher's exact test and t-test, as appropriate. Differences in adherence to duration of hand hygiene will be calculated for both intervention and control groups. As a secondary outcome for Aim 1, the investigators will assess changes and differences in hand hygiene perception based on responses to select questions from the PSHW. For Aim 2, mindfulness will be based on responses to the FFMQ and well-being will be based on responses to the WBI. Survey scales will be scored according to the published algorithms. Descriptive statistics will be used to summarize participant scores from baseline and post-intervention, as well as 6-month post-intervention (sustainability) follow-up assessments. Within-group paired-samples t-tests will be used to test for improvement in participant scores across the baseline, post-intervention (~14 days for physicians and 1-month for nurses), and 6-month post-intervention (sustainability) follow-up periods, for the intervention and control groups separately. Participants not completing all surveys will still be included in any analysis for which they provide data. Listwise deletion for observations containing less than 85% complete responses for the FFMQ or WBI items will be used. Missing values for observations with at least 85% responses for the FFMQ or WBI items will be imputed using the average value obtained from non-missing values within each respective subscale. Multilevel linear mixed regression models will be used to assess changes in mindfulness and well-being across groups and the effectiveness of the intervention. Mixed models account for correlation between repeat measurements on the same participant and accommodate missing data across time points. Random effects will be modeled to account for clustering of survey responses at the clinician level. All models will be adjusted for fixed effects for clinician role (physician/nurse) and intervention fidelity. For all analyses, p-values less than 0.05 will be considered significant and all tests will be two-tailed.

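### The run-in month gives every nursing unit a hand hygiene baseline, but no planned analysis uses it, so chance unit differences stay in the 3 v 3 nurse estimate

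*Protocol*

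**What the plan says.** **Baseline collected.** Protocol 5.1 (Habituation Period) gives the purpose of the run-in month: "To collect baseline data on hand hygiene adherence and duration and to habituate providers to the presence of observers". For nurses, Protocol 5.1 (Data Collection and Management) adds: "Observations will be conducted for 1 month before the intervention and 1-month after the intervention", and on coverage: "On all participating units, observations of nurse hand hygiene while entering and exiting patient rooms will be conducted". Table 2 shows only one month of nurse observation before the intervention, so I take these to be the same month.

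**Units.** Table 2 lists "2 units (1 intervention; 1 control) at Ann Arbor VAMC & 4 units (2 intervention; 2 control) at MEDVAMC randomized once", which is three units per arm, balanced within site.

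**Volume.** The Data Collection text expects "approximately 80 hand hygiene moments observed per day per unit" and continues: "Observing 3 units per arm for approximately 44 days total would lead to an estimated 7,040 nurse hand hygiene observations per study arm in total".

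**Analysis.** The Aim 1 model in Protocol 5.6 is a Poisson model with robust variance. Its stated terms are arm, provider type and level, and clustering by team or nursing unit. Its test is: "Statistical significance will be calculated for the intervention (intervention vs. control) coefficient". The SAP says of hand hygiene: "Differences in hand hygiene adherence and duration between intervention and control groups will be assessed using Fisher's exact test and t-test, as appropriate". It states no clustering and no baseline for this outcome. Survey scores are treated differently: Protocol 5.6 adjusts them for the pre-test score, and the SAP models mindfulness and well-being over time.

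**The concern.** The trial measures each unit's adherence and duration before anyone is treated, and then leaves that measurement out of every stated comparison of its Aim 1 primary outcomes. The secondary survey outcomes do get a baseline adjustment. The power paragraph in Protocol 5.6 also frames the target as a rise from a baseline level, and the pilot results in Table 1 are reported as change from baseline by arm.

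With one unit against one at Ann Arbor and two against two at Houston, randomisation leaves much to chance. If the intervention units happen to start several points above or below their site's control units, that gap passes into the nurse estimate at full size. Nothing in the planned output would show how much of the estimate it accounts for. Precision and protection against chance imbalance are at stake, in a comparison that has little of either.

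**Working it through.** **1. The plan's own count.** 80 moments x 3 units x 44 days = 10,560 per arm, not 7,040. The stated figure equals 80 x 2 x 44. Taking half of the 44 days as the post-intervention month gives 80 x 22 = 1,760 moments per unit-month. Working back from 7,040 gives 7,040 / (3 x 2) = about 1,173. The choice hardly matters below, because variation between units dominates.

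**2. Terms in each stated analysis.**

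| Analysis | Arm | Unit clustering | Unit baseline or period |
|---|---|---|---|
| Protocol 5.6, hand hygiene model | yes | yes | none stated |
| SAP, hand hygiene tests | yes | none stated | none stated |
| Protocol 5.6, survey ANCOVA | yes | none stated | pre-test score |

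**3. Chance spread of the 3 v 3 difference, post-intervention month only.** Let p = 0.80 (the power paragraph's baseline level), n = 1,760, equal unit weights, and ICC = the intraclass correlation between units within a site. The documents give only a pooled ICC of 0.4 across site, team and unit, so smaller values are assumptions.

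SE = sqrt( (2/3) x [ICC x p(1-p) + (1-ICC) x p(1-p)/n] )

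- ICC 0.01: sqrt((2/3) x [0.0016 + 0.00009]) = 3.4 points (also 3.4 with n = 1,173)
- ICC 0.05: sqrt((2/3) x [0.0080 + 0.00009]) = 7.3 points
- ICC 0.10: sqrt((2/3) x [0.0160 + 0.00008]) = 10.4 points
- ICC 0.40: 20.7 points, an upper case, because 0.4 may include site variance that the within-site allocation largely removes

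The smallest planned effect is 88 - 80 = 8 points. It is a whole-trial assumption, not one for nurses alone. With no true effect, the probability of a chance difference of at least 8 points, 2 x [1 - Phi(8/SE)], is 1.7%, 28%, 44% and 70% respectively.

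**4. Effect of using the baseline.** Let r be the correlation of a unit's true rate between the two months. The documents do not give it. The between-unit SE is multiplied by:

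| r | Baseline covariate, known slope: sqrt(1 - r^2) | Change contrast: sqrt(2(1 - r)) |
|---|---|---|
| 0.3 | 0.95 | 1.18 |
| 0.5 | 0.87 | 1.00 |
| 0.7 | 0.71 | 0.77 |
| 0.9 | 0.44 | 0.45 |

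At ICC 0.05, with sampling error included, the 7.3 points become 6.4, 5.3 and 3.3 by covariate and 7.4, 5.8 and 3.4 by change contrast, at r = 0.5, 0.7 and 0.9. The covariate figures treat the slope as known. With six units it must be estimated, so the real gain is smaller.

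**5. What remains.** There are 2 x 6 = 12 possible within-site allocations, so the smallest two-sided permutation p-value is 2/12 = 0.167, with or without a baseline.

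**The case against.** **Randomisation and clustering already deal with unit differences.** In part. Allocation within site makes the estimate unbiased in expectation and largely cancels site differences. The clustering term in Protocol 5.6 is meant to put unit variation into the standard error, although it is unreliable with six units. Neither takes a realised gap between units out of the estimate. A reader might infer that the nurse result is biased. The documents do not support that: the problem is chance imbalance and lost precision.

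**Pre-intervention days may count as outcome.** A reader might infer from the 44-day total that the two months are pooled, so that a true 8-point effect would appear as (0 + 8)/2 = 4 points. The documents do not say this. The 44 days belong to an estimate of data volume. The power paragraph names the measurement time points as intervention and follow-up, and Table 2 places the outcome observations at the intervention assessment. What stands is that the outcome month should be named.

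**The risk-difference sentence in Protocol 5.6 could mean pre/post change.** It does not mention baseline and feeds no comparison between arms.

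**The size rests on undocumented inputs, and the run-in is also a habituation month.** Both are fair. Many moments per unit reduce sampling error but say nothing about whether a unit's true rate is stable from month to month. If units habituate to observers at different speeds, r falls and a change contrast could add noise. This is why no single gain is claimed and why a change contrast is not preferred over a baseline covariate.

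**Conclusion.** The point holds for the nurse part of Aim 1. A baseline for adherence and duration is planned on all six units, and no stated hand hygiene analysis uses it. Chance differences between units within a site therefore stay in the 3 v 3 estimate.

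The possible gain runs from small to large. The between-unit standard error falls by about 13%, 29% or 56% with a known-slope covariate, and by 0%, 23% or 55% with a change contrast, at assumed r of 0.5, 0.7 or 0.9. Below r = 0.5 the change contrast loses precision. The figures in points rest further on assumed ICCs. That the baseline goes unused does not depend on any of these assumptions.

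The conclusion does not reach physicians. Their teams turn over every 2 to 4 weeks across 12 months, so the run-in month is not a baseline for the teams later randomised. Nor would using the baseline make six units enough.

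**What to change.** In Protocol 5.6 and the SAP, for nurse adherence and duration:

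1. State that the post-intervention month is the outcome and that pre-intervention days are not outcome observations. Split the 44-day total in Protocol 5.1 by period and correct its arithmetic.
2. Bring each unit's run-in rate into the analysis at unit level and prespecify one form: a baseline covariate, or an arm-by-period term with unit effects. Individual-level adjustment is not available, because nurse observations carry unit and role but no names.
3. Use the same run-in month as the reference for the 12-month assessment.
4. Tabulate run-in adherence and duration by unit and arm.
5. State that physician results are concurrent between-arm comparisons.

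**Cost.** Wording only, since the observations are already planned. The covariate's slope will be poorly estimated with six units. The change contrast loses precision if r is below 0.5, which is more likely over the 12-month gap. The SAP is dated December 2025 and the documents do not say how far data collection has gone. If results by arm have already been seen, the baseline-adjusted analysis should be labelled as added afterwards and shown beside the analysis now planned.

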Randomization – At each study site the participating physician teams and nursing units will be randomly assigned into one of two study arms (intervention/control). For physician teams, this will occur on a rolling basis for 12 months with 2 physician teams randomly selected at each site each month for participation (1 intervention, 1 control). Once randomized, an email will be sent to the initial attending of the team introducing the study and asking them to reply to the email if they would prefer to opt out and not have their team participate in the randomized controlled trial. If the attending physician from a team refuses to allow their team to participate, the next team identified from the randomized list will be approached to participate. If a new attending joins the team mid-month, they will be approached to participate in the study, but will be automatically assigned to the same randomization group as the rest of their team.

Similarly, a total of 2 medical/surgical units from VAAHS (1 intervention, 1 control) and 4 medical/surgical units from MEDVAMC (2 intervention, 2 control) will be randomly selected to participate in the nurse portion of the project. The nurse manager for each

selected unit will then be approached to obtain approval for the unit to participate. If a nurse manager declines, the next unit on the list will be selected.

For both physicians and nurses, an independent statistician will allocate the teams and units in a concealed fashion, using a computer-generated randomization schema. The physicians and nurses from the intervention groups will receive both independent and group-facilitated mindfulness education, will be encouraged to use a mindfulness mobile app as a practice reminder and additional resource, and instructed to integrate moments of mindfulness with repeated episodes of hand hygiene during the course of caring for patients. The control groups will receive no such education or intervention and will continue as usual.

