 - Nurses on intervention units will be sent an introductory email (**Appendix J**) with information about the study and asking to set up a time and place to discuss the study in more detail. If we are unable to reach the nurses through email, study staff will approach the nurses during their work shift and ask to set up a time to meet to discuss the study in private. Recruitment will occur in a private room or office using the attached recruitment script (**Appendix K**).
- Physicians: We estimate enrolling approximately 35 attending physicians, 24 senior residents, and 48 intern physicians into each arm of the study, which will result in a total of 214 physicians in total. All physicians from physician teams will be asked to participate in the randomized controlled trial and provide a signed informed consent. Each month one team at the Ann Arbor VAMC and 2 teams at MEDVAMC will be randomized to intervention and an equal number at each site will be randomized to control. A flyer describing the study (**Appendix S**) will be emailed (**Appendix T**) to teaching attendings to introduce the study. Before the beginning of the month, the initial attending physician on each selected team will be sent an email describing the study and giving them the option to opt out of their team being approached to participate (**Appendix L**). A time and place will be scheduled to discuss the study in more detail and obtain informed consent from the attending (**Appendix M**). Unless the attending indicates they do not want their team participating, the rest of the team will be sent an email describing the study (**Appendix L**). Then study staff will approach the senior resident and interns in the team rooms and ask to speak with them about the study (**Appendix M**). If there are others in the team room, the study staff will ask the residents to follow them to a private room to discuss the study in greater detail. If they are willing to participate, they will be asked to sign an informed consent document. The primary participants are the attending physicians on each team. If the initial attending declines allowing their team to participate, another team will be randomly selected and approached for participation. If any physicians choose to not participate, they will not be asked to participate in the intervention activities (if randomized to the intervention) or to complete the study surveys (both study

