arms). However, hand hygiene data will still be collected using a waiver of informed consent. When a new attending starts on a team that has already been randomized, they will be recruited in a similar manner as the initial attending (email, followed by in person recruitment). If the 2nd attending on the team declines participation, the team is still considered enrolled, however the new attending will not be asked to participate in the intervention (if on an intervention team) or complete the study surveys.

Aim 3: Interviews and Guided Discussions

- Interviews: Select participants in the intervention arm will be asked to participate in the qualitative evaluation interviews to provide feedback about the intervention. We estimate enrolling 4-6 nurses and 8 physicians from each site. The providers will be recruited via email (**Appendix N**) or in-person communication with study staff. If they agree, a day, time, and location for the interview will be arranged. At the Ann Arbor VAMC, these interviews can be conducted in person, or by phone if needed. Members of the team from Ann Arbor plan to travel to MEDVAMC to conduct these interviews in person as well, since more information can be obtained through direct observation and face to face interactions. However, if travel restrictions are in place or if someone is unable to attend an in-person meeting, the interview can be scheduled to occur either over the phone or using a VA approved conferencing program like Microsoft Teams or Zoom for Government. The Ann Arbor qualitative team will provide a study information letter and review the purpose of the interview before obtaining verbal informed consent. As we will be audio recording – will ask verbal permission to audio record at the start of the interview using the attached audio recording permission script (**Appendix O**). We will ask for a waiver of informed consent for this aim of the study as it poses minimal risk and a signed consent would be the only link between the subject and their interview, which would increase their risk of loss of confidentiality.

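### Physician teams and nursing units are randomised before their attending or manager agrees, and refusers are replaced; the arm should be released only after agreement, above all for nursing units

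*Protocol*

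**What the plan says.** **Physician teams.** Protocol 5.1 (Randomization) has two teams per site per month drawn, one for each arm. Then: "Once randomized, an email will be sent to the initial attending of the team introducing the study". The same message offers a way out for the whole team, "asking them to reply to the email if they would prefer to opt out and not have their team participate". If the attending refuses, "the next team identified from the randomized list will be approached to participate". Section 5.2 puts the replacement step slightly differently: "If the initial attending declines allowing their team to participate, another team will be randomly selected and approached for participation".

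**Nursing units.** Section 5.1 has two units at Ann Arbor and four at MEDVAMC selected, with the number per arm given. Approval from the manager comes only afterwards: the "selected unit will then be approached to obtain approval for the unit to participate". A refusal again leads to replacement, as 5.1 states: "If a nurse manager declines, the next unit on the list will be selected".

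**Concealment and consent.** Section 5.1 says that "an independent statistician will allocate the teams and units in a concealed fashion". Under 5.3, physicians in both arms sign one form that describes both arms, and the research assistants taking consent are blinded to the physicians' arm. For nursing units, 5.1 and 5.3 say that the research assistants do know the arm. Control nurses consent by returning a survey, while intervention nurses give written consent.

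**Who is observed and analysed.** Section 5.2 (Aim 1) seeks the consent waiver for covert observation of units and teams that take part in the trial. Neither Protocol 5.6 nor the SAP says that clusters are analysed as allocated. Neither plans a record of refusals by arm or a related sensitivity analysis.

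**The concern.** If the person deciding for a cluster knows or can guess the arm, the clusters that remain in the two arms are no longer alike in expectation. Replacing the refuser keeps the numbers up but does not restore the comparison.

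The conditions for this are most plausible for nursing units. Control nurses only complete three surveys. Intervention nurses are asked to sign consent, complete three modules, consider an app and attend weekly discussions of up to 30 minutes. The protocol itself expects burden to affect participation: 5.3 gives that as the reason for the lighter consent in control units. There are three units per arm, so one arm-driven replacement changes a third of a nurse arm.

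For physician teams one specific route stands out. Section 5.4 lets attendings take part in several months but bars them from the control arm once they have been in the intervention arm. An attending approached again after an intervention month can therefore work out the arm before deciding.

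**Working it through.** The plan states no figure on this point, so the main check is of the order of steps. The arithmetic only shows what arm-dependent refusal could do.

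**Order of steps**

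| | Physician teams | Nursing units |
|---|---|---|
| Randomised before agreement | Yes (5.1) | Selected with numbers per arm, manager asked next (5.1) |
| Refuser replaced | Yes (5.1, 5.2) | Yes (5.1) |
| Staff taking consent know the arm | No (5.3) | Yes (5.1, 5.3) |
| Consent differs by arm | No (5.3) | Yes (5.2, 5.3) |
| Arm stated to be withheld until agreement | Not stated | Not stated |

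**Bias formula.** Let a share r of an arm's clusters refuse, and let refusers' adherence be d points below that of accepters, whose mean is a. The mean as randomised is (1 - r)a + r(a - d) = a - rd. After replacement by accepters the arm mean is a, which is too high by rd. Hence

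bias = r_I × d_I - r_C × d_C.

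**Scale.** Inputs from 5.6: baseline adherence 80%, expected 88%-92% (an effect of 8-12 points), N = 334, 60 opportunities per provider, ICC 0.4. The design effect, with the provider as cluster, is 1 + 59 × 0.4 = 24.6. Effective size per arm is 167 × 60 / 24.6 = 407. SE = sqrt(2 × 0.8 × 0.2 / 407) = 2.8 points. Type I error is Φ(bias/SE - 1.96) + Φ(-bias/SE - 1.96).

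**Scenarios.** All values of r and d are assumptions; the documents give none.

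| Refusal, intervention / control | d (points) | Bias (points) | Share of 8-point effect | Type I error |
|---|---|---|---|---|
| 10% / 10% | 10 in both | 0 | 0% | 5.0% |
| 10% / 5% | 10 in both | 1.0 - 0.5 = 0.5 | 6% | 5.4% |
| 20% / 5% | 10 in both | 2.0 - 0.5 = 1.5 | 19% | 8.3% |
| 30% / 5% | 10 in both | 3.0 - 0.5 = 2.5 | 31% | 14.5% |
| 20% / 5% | 20 in both | 4.0 - 1.0 = 3.0 | 38% | 18.8% |
| 30% / 5% | 20 in both | 6.0 - 1.0 = 5.0 | 63% | 43% |
| 20% / 20% | +10 / -10 | 2.0 + 2.0 = 4.0 | 50% | 29.7% |

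These are illustrations, not bounds. For example, 30% against 0% with d = 20 gives 6 points, and heavier refusal in the control arm reverses the sign. The bias column does not depend on the SE, but the type I column does. If clustering by team or unit makes the SE larger, the inflation is smaller. With 327 per arm instead of 407, the 1.5-point and 5-point rows give 7.7% and 35.9%.

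**Nursing units.**

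- Spare units (5.1): Ann Arbor 3 - 2 = 1, MEDVAMC 5 - 4 = 1. A second refusal at a site cannot be replaced.
- Chance that at least one of six units refuses, at an assumed rate per unit: 1 - 0.95^6 = 26% at 5%; 1 - 0.90^6 = 47% at 10%; 1 - 0.80^6 = 74% at 20%.
- One replaced intervention unit is 20 of 60 nurses. If the replacement differs by 0-20 points, the nurse contrast shifts by 0-6.7 points (20/3). Pooled with physicians and weighted by provider, the shift in that arm is 20/167 × 0-20 = 0-2.4 points.

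**The case against.** **Physician teams.** Allocation is concealed, the staff taking consent are blinded, and one form describes both arms. If the attending opts out without knowing the arm, replacing the team amounts to randomising among willing teams. That narrows generalisability but does not bias the comparison. This stands, and it makes the physician risk the smaller one. It does not close it: the plan never says when concealment ends, and the re-approached attending remains.

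**Nursing units.** No sentence says that the manager is told the arm; the text says only that research staff know it. The section also opens by speaking of participating teams and units being assigned, which could suggest agreement came first. The detailed steps say otherwise, and nothing says the arm is withheld from the manager. Arm-dependent refusal is therefore plausible but not demonstrated. The burden should not be overstated either: modules are done off duty with payment, and discussions are offered, not required.

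**Existing protections.** Individual physicians who decline within an enrolled team stay in the primary outcome: "However, hand hygiene data will still be collected using a waiver of informed consent". A reader might infer from this that a refusing team or unit could also be observed under the existing waiver. The documents do not support that. The sentence concerns individuals, and 5.2 limits the waiver to units and teams in the trial. For nursing units, the pre-intervention month of observation would make a baseline imbalance visible, but the model in 5.6 does not adjust for baseline adherence.

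**Conclusion.** The point holds as a gap in the order of steps. Clusters are randomised, then asked, and refusers are replaced and leave the comparison, with no as-allocated analysis planned. The exposure is mainly in the nursing units, and secondarily in physician teams whose attending can learn or infer the arm.

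In the scenarios worked, bias runs from 0 to about 5 points against a planned 8-12. It is zero when refusal and the kind of refuser are the same in both arms. These figures rest on assumed refusal rates and assumed differences between refusers and accepters.

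A reader might go further and conclude that the comparison of both physicians and nurses is already broken, or that managers approve a workload they know. The documents show the opportunity for arm-dependent selection, not its occurrence, and for physicians they contain real safeguards.

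**What to change.** Amend Protocol 5.1 and 5.2 as follows.

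1. Obtain nurse-manager approval for all candidate units, and attending opt-outs for each month's candidate teams, before allocation. The independent statistician then randomises among those that agreed. Alternatively, keep the present order but state that the arm is released only after agreement is settled.
2. Log any later refusal and replacement by arm and site, and report the log.
3. State in 5.6 and the SAP that every agreed cluster is analysed in its allocated arm, with a sensitivity analysis if any replacement followed release of the arm.
4. Use one replacement rule. Section 5.1 takes the next team on the list, whereas 5.2 selects another at random. The two sections also differ on MEDVAMC intervention teams per month (one or two).

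The cost is slightly earlier contact with managers and attendings and a short amendment. Section 5.2 already places the attending email before the month starts. Observing clusters that refuse is not part of this proposal: it would need a wider waiver and possibly more observer time. The SAP is dated December 2025. If recruitment is already complete, reporting refusals by arm, stating when the arm was disclosed, and the sensitivity analysis remain possible to the extent that records exist.
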